Study protocol and statistical analysis plan

Evaluation of the course and effectiveness of conservative therapy in patients with Achilles tendinopathy

NCT number: NCT05702918

Date: March 28, 2022

(Date of approval of the project by the ethics committee)

Study design and description

This work is designed as a randomized clinical trial, in which the effects of a protocol of 12-week resistance training loading the Achilles tendon and low-energy focused extracorporeal shock wave therapy (ESWT) in patients with Achilles tendinopathy (AT) will be monitored. It is estimated that at least 40 patients will participate, randomly divided into two groups. Group A will be instructed to perform a training protocol in combination with ESWT according to selected parameters. Group B only completes the same training protocol.

The research within one patient will last a total of 26 weeks from the initial to the final examination and will include several control measurements: at 6, 12, and 26 week from the beginning of therapy. Potential participants will be selected based on the recommendation of a specialist doctor and their suitability will be assessed according to the inclusion criteria. They will then be invited to an initial examination. This will include an objective examination by a physiotherapist, a subjective assessment by the patient and an ultrasonographic (USG) examination followed by a micromorphological analysis using special software. At the end of the initial examination, the participant will be randomly assigned to group A or B. Group A will follow resistance training protocol and receive ESWT. Group B will follow resistance training only. The study program for a specific participant will depend on the assigned group.

Patient selection

Inclusion criteria: age 18–50 years; localized Achilles tendon pain limiting daily or sports activity; clinical manifestation of AT confirmed by a clinician; and unilateral symptoms.

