After that, the preset will be changed to the specific setting, and three pictures will be saved in long axis for subsequent micromorphological analysis using SFA. SFA is a non-invasive, specialized method which analyzes the US image *in vivo*. In particular, it analyzes the anisotropic B-mode speckle pattern arising from within a tissue type in the spatial frequency domain and is capable of detecting and comparing collagen fascicles organization, spacing, and density across various parameters. Mean of those three values will be used for statistical analysis.

ESWT application

The low-energy focused ESWT will be applied using the BTL-6000 FSWT machine with piezoelectric generator and a coupling pad which modulates penetration depth to 0-35 mm. The setting is chosen based on ISMST guidelines (<https://shockwavetherapy.org>): Energy Flux Density (EFD) between 0.10-0.15 mJ/mm² due to patient tolerance, frequency at 5 Hz. A total of 2000 shocks will be applied semi-statically to the most US defined pathological tendon area using a contact gel. The set parameters will not change during the study and will remain the same for each patient.

Data analysis

The normality of the data distribution will be determined by calculating the Shapiro-Wilk p value. Independent t-tests (or Mann Whitney U tests for non-parametric) will be performed for each parameter to compare baseline values between groups. In addition, paired t-tests (or Wilcoxon tests) will be performed for each parameter, evaluated in each group separately between baseline and final values. To reach effect size, Cohen's d will be calculated for paired t-tests and biserial rank correlation for non-parametric Wilcoxon test.

Intergroup statistical significance between baseline and follow-up values of morphological parameters will be evaluated using two-way ANOVA with repeated measures or non-parametric Friedman test. Statistical significance is set to $p < .05$.

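### A Shapiro-Wilk p value selects the test and the effect-size metric for each within-group comparison, and nothing requires the two arms of an outcome to get the same choice

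*Combined protocol and SAP*

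**What the plan says.** All the relevant text is in the Data analysis section of the combined protocol and SAP.

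- **Normality check:** "The normality of the data distribution will be determined by calculating the Shapiro-Wilk p value". No cut-off is given for this check. The general significance level is 0.05.
- **Within-group tests:** "paired t-tests (or Wilcoxon tests) will be performed for each parameter, evaluated in each group separately between baseline and final values".
- **Effect size follows the test:** "Cohen's d will be calculated for paired t-tests and biserial rank correlation for non-parametric Wilcoxon test".
- **Between-group follow-up analysis:** "Intergroup statistical significance between baseline and follow-up values of morphological parameters will be evaluated using two-way ANOVA with repeated measures or non-parametric Friedman test". This sentence covers morphological parameters only. The other between-group tests in the section (independent t-test or Mann-Whitney) compare baseline values.

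The Study design and description section gives the size: "It is estimated that at least 40 patients will participate, randomly divided into two groups". The allocation ratio is not stated. VISA-A and NRS pain are collected under Initial and final examination. For them, the within-group tests and effect sizes are the only outcome analysis described.

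**The concern.** The trial is randomised to compare training plus ESWT with training alone. Under the plan, a preliminary test on small samples decides three things: which test is used, whether it addresses a mean or a rank shift, and on which scale the effect is reported. The choice sits inside a clause about tests run group by group, and no sentence ties the two groups together. One arm could therefore be reported with a t-test and Cohen's d, and the other, for the same outcome, with a Wilcoxon test and a rank-biserial correlation.

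Those two effect sizes cannot be set side by side. For VISA-A and NRS this matters most, because setting the arms side by side is the only A-versus-B reading that the plan offers.

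A second consequence concerns the morphological parameters. The Friedman test ranks repeated measurements within subjects and has no group factor. If non-normality sends the analysis there, the A-versus-B comparison is lost.

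The plan also does not say what is checked for normality. The paired t-test depends on the distribution of the differences and the ANOVA on its residuals. Checking raw values at each visit can give a different answer.

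**Working it through.** The plan gives no figure on this point, so there is none to reproduce. The check sizes the consequence under stated assumptions.

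**Inputs**
- At least 40 patients in two groups (Study design and description). Assumed: equal allocation, so about 20 per arm, with 15 to 25 as a range.
- Shapiro-Wilk cut-off of 0.05. Assumed, borrowed from the plan's general significance level.
- Normality judged separately in each arm. Assumed; the plan does not say.
- Means, SDs and a baseline–final correlation of 0.5 for NRS and VISA-A. Assumed; the documents give none.

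**Step 1. Chance that the arms get different tests, exactly normal differences.** If each arm is rejected with probability p, and both arms have the same distribution, P(different tests) = 2p(1 − p).
- One check on the differences, p = 0.05: 2 × 0.05 × 0.95 = 9.5% (simulated at 20 per arm: 9.1%).
- Checks on the raw baseline and final values, either rejecting, treated as independent: p = 1 − 0.95² = 0.0975, so 2 × 0.0975 × 0.9025 = 17.6%. Simulation with correlation 0.5 gives 18–19%.

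In these cases every rejection is a false alarm.

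**Step 2. Other shapes, one check per arm.** The simulated rejection rate is put into the same formula, 20 per arm.

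| Assumed distribution | Rejection rate | Arms differ |
|---|---|---|
| t, 5 df | 0.192 | 31% |
| Gamma, skewness 1 | 0.289 | 41% |
| Lognormal, sigma 0.5 | 0.525 | 50% |
| Rounded 0–10 scale | 0.133 | 23% |
| Score capped at 100 | 0.351 | 46% |
| Exponential | 0.833 | 28% |

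Across these shapes and the normal, with 15 to 25 per arm, the range is 9% to 50%. The rate peaks when rejection is near one half and falls again when non-normality is obvious in both arms.

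**Step 3. Bounded outcomes, baseline and final simulated together, 20 per arm.** NRS was taken as an integer scale falling from 6 to 2 or 3 (SD about 2). VISA-A was taken as rising from 55 to between 75 and 88 (SD 12 to 15), capped at 100.

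| Outcome | Arms differ, checked on differences | Arms differ, checked on raw values |
|---|---|---|
| NRS | about 26–31% | about 43–47% |
| VISA-A | about 9–10% | about 17–50% |

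The wide VISA-A range comes from the ceiling. Raw-value discordance is about 49% with a final mean of 88 (SD 15), 29% with 80 (SD 15) and 17% with 75 (SD 12).

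**Step 4. Does it matter what is checked?** The choice between raw values and differences changes the selected test in about 13–14% of arms with normal data and in roughly 40–60% for NRS. For VISA-A the figure runs from about 13% to more than 50%, again depending on the ceiling.

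**Step 5. Are the two effect sizes interchangeable?** Simulated normal paired differences, 20 patients:

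| True standardised change | Mean Cohen's d | Mean rank-biserial |
|---|---|---|
| 0.5 | 0.52 | 0.51 |
| 0.8 | 0.84 | 0.73 |
| 1.2 | 1.25 | 0.90 |
| 2.0 | 2.08 | 0.99 |

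They agree for small changes and separate for large ones, because the rank-biserial correlation cannot exceed 1. Two arms with the same true change of 2.0 could be reported as about 2.1 and 1.0.

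**The case against.** The strongest reply is that a per-arm normality check is an inference. The group-by-group wording describes the paired tests, not the Shapiro-Wilk step. A single decision per parameter, applied to both arms, is also consistent with the text, and then the arms cannot diverge. This stands: a reader might infer that the plan prescribes normality testing in each arm, or on raw values, and it states neither. The percentages above are therefore conditional. What does not fall is that nothing in the plan rules divergence out. Even a pooled check would leave the test, the hypothesis and the effect-size scale to be settled by the data.

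A reader might also infer a serious inflation of false-positive findings. The choice between a t-test and a Wilcoxon test has only a small effect on type I error, so the point does not rest on that. Nor is it right to count normality rejections over all four visits, since the paired tests use only baseline and final values.

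It is also fair to say that within-group effect sizes are not the A-versus-B test, that morphological parameters have a named between-group analysis, and that the larger gap for VISA-A and NRS is the lack of one. That limits the harm but does not remove it. Those two outcomes have nothing else to rely on, and the protection for morphological parameters fails if the Friedman fallback is used. The plan does not spell out what triggers that fallback, but the normality check is the only criterion it gives.

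**Conclusion.** The point holds as a defect of an incompletely specified, data-driven rule. With judgement per arm at 0.05 and about 20 patients per arm, the arms would be reported with different tests and effect-size scales for about 9.5% of outcomes under exact normality. Under the assumed bounded scales the figure is about 9–31% if differences are checked and about 17–50% if raw values are checked. Only the 9.5% is analytic, and it too depends on the per-arm assumption. The rest moves with the assumed means, SDs and ceiling.

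The damage is to comparability between arms and to having one pre-stated analysis. It falls mainly on VISA-A and NRS, and on morphological parameters if their analysis moves to Friedman. The change is worth making, but the issue does not by itself invalidate the trial.

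**What to change.** Remove the Shapiro-Wilk gate from the Data analysis section and replace it with the following, fixed before outcome data are examined.

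1. For each outcome, including VISA-A and NRS, name one analysis to be used whatever the normality result: the baseline-adjusted difference, A minus B, with a 95% confidence interval in scale units.
2. If within-arm changes are also shown, use the same test and the same effect-size metric in both arms.
3. Judge fit from the model residuals.
4. Report one fixed rank or permutation sensitivity analysis of the between-group comparison for every outcome, whatever the residuals show. Do not use Friedman for this purpose, since it has no group factor.

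Once the choice is fixed in advance, the chance that the arms receive different tests or metrics is zero by construction.

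The cost is revised SAP wording and one additional run per outcome. The main drawback is that model-based intervals are approximate for a strongly skewed outcome at about 20 per arm. The sensitivity analysis checks the between-group conclusion but does not cover intervals for change within an arm.

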Exclusion criteria: professional or high-volume recreational sports (>4 sessions/week, >1h each); contraindications to ESWT according to International Society for Medical Shockwave Treatment (ISMST) guidelines at <https://shockwavetherapy.org>; previous symptomatic mechanical tendon injury (partial/complete rupture); history of contralateral AT; neurological, metabolic, oncologic, or systemic disease (e.g., diabetes, neuropathy, lupus, spondyloarthritis, rheumatoid arthritis); AT-specific treatment within the past 6 months; or use of anticoagulants or statins.

Initial and final examination

During the initial and final examinations, the several tasks to the patient will be performed. Firstly the anamnestic data will be collected, then the area of greatest pain will be localized by palpation.

Secondly, the patient will be asked to complete a validated Victorian Institute of Sports Assessment - Achilles (VISA-A) questionnaire, which assesses the subjectively perceived severity of the disease and partly its impact on the quality of normal daily or sports activities.

The patient's maximal pain will be assessed using a standardized numerical rating scale (NRS) of pain. The patient will be asked about the morning and maximum pain that could be caused by various factors.

Lastly, the ultrasonographic (US) examination and subsequent software analysis using Spatial Frequency Analysis (SFA) of patient's AT in both legs will be performed. This examination is described in the following chapter.

Both, initial and final examinations in each patient will be performed by only one person (the investigator of the study).

Ultrasonographic examination

Ultrasound imaging will be performed by the same experienced examiner using a linear probe (L12-3E, 12 MHz) on a Mindray DC-70 system in MSK preset (B-mode). The participant will be placed in the prone position with the knee in an extended position and the ankle passively maintained in neutral position. The midportion of the Achilles tendon will be evaluated from the

myotendinous junction to the upper border of calcaneus. The probe will be placed as parallel to the tendon fibers as possible, and the image capture will be always carefully performed to ensure optimal image quality and minimize movement artifacts.

The values of anteroposterior tendon width at the anteroposterior widest point will be collected using the measuring instruments included in USG machine.

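### The plan names no primary outcome, deciding visit, multiplicity rule or success criterion, and its only between-group follow-up test covers an open number of morphological parameters, leaving out VISA-A and pain

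*Combined protocol and SAP*

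**What the plan says.** The measurements come from two sections.

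- **Initial and final examination:** "the patient will be asked to complete a validated Victorian Institute of Sports Assessment - Achilles (VISA-A) questionnaire". For pain, "The patient will be asked about the morning and maximum pain that could be caused by various factors". That makes one questionnaire score and two pain ratings.
- **Ultrasonographic examination:** tendon width, plus SFA outputs describing fascicle "organization, spacing, and density across various parameters". The outputs are neither listed nor counted, and no direction of improvement is given for any of them.

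The Data analysis section then plans three kinds of test.

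- **Baseline, between groups:** independent tests "will be performed for each parameter to compare baseline values between groups".
- **Within groups:** "paired t-tests (or Wilcoxon tests) will be performed for each parameter", run in each group on its own and comparing baseline with the final value.
- **Follow-up, between groups:** "Intergroup statistical significance between baseline and follow-up values of morphological parameters will be evaluated using two-way ANOVA with repeated measures", with a Friedman test as the non-parametric alternative.

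One threshold closes the section: "Statistical significance is set to" p < .05. The Study design and description section sets visits at weeks 6, 12 and 26, the last being the final examination, and a minimum of 40 patients randomised to two groups. None of these sections calls an outcome or visit primary, adjusts for multiple tests, or says what result would count as effectiveness.

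**The concern.** The title promises an evaluation of effectiveness, and the design randomises patients to training with or without shock wave therapy (ESWT). The question is therefore what ESWT adds, and only a between-group comparison after treatment answers it. Two gaps follow from the text.

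1. The planned comparison covers morphology only. Symptoms and tendon structure can move differently. As written, a group difference in one SFA output could carry the effectiveness claim while VISA-A and pain were never compared between groups at follow-up.
2. Within morphology, any of several unadjusted tests could carry the claim. Because no SFA parameter is named in advance and no direction of benefit is stated, a significant change either way could be presented as improvement. The plan also does not say which visits enter the ANOVA, or whether the group, time or interaction term decides.

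At stake are the error rate of the main claim and whether that claim concerns anything patients report.

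**Working it through.** **Plan's own figure.** The plan states no family-wise error rate, so there is none to reproduce. The sample size of at least 40 cannot be reproduced either, because no effect size, SD or power is given.

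**Inputs**
- Per-test level: 0.05 (Data analysis). Two-sided testing is assumed.
- Outcomes named: VISA-A, morning pain, maximum pain, tendon width, which is 4.
- SFA parameters: plural, number not stated. Two or three are assumed here, so two gives 4 + 2 = 6 outcomes in total.
- Morphological parameters, read as width plus SFA outputs: 1 + 2 = 3 or 1 + 3 = 4.
- Group size: 20 each, assumed from a minimum of 40; the allocation ratio is not stated.

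**Which tests bear on ESWT**

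| Outcome | Baseline, between groups | Within group, baseline to final | Follow-up, between groups |
|---|---|---|---|
| VISA-A | yes | yes | none stated |
| Morning and maximum pain | yes | yes | none stated |
| Tendon width | yes | yes | ANOVA or Friedman |
| SFA outputs (number open) | yes | yes | ANOVA or Friedman |

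Only the last column can show an ESWT effect. Both groups train, so change from baseline is expected in both, and a significant paired test does not separate ESWT from training. Nor does significance in one group but not the other. If both groups truly change equally and each paired test has an assumed 80% power, that pattern occurs with probability 2 × 0.8 × 0.2 = 32% for a single outcome.

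**Chance of at least one false positive among k between-group tests**, one deciding test per parameter and no true group difference. If independent, it is 1 − 0.95^k:
- k = 3: 1 − 0.95³ = 14.3%
- k = 4: 1 − 0.95⁴ = 18.5%
- k = 6: 1 − 0.95⁶ = 26.5%

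For equally correlated normal test statistics (correlations assumed):
- k = 3: about 13.5% at correlation 0.3 and 12.5% at 0.5
- k = 6: about 24% at 0.3 and 21% at 0.5
- At a correlation of 0.7 these fall to about 11% (k = 3) and 16–17% (k = 6).

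The k = 3 and k = 4 cases correspond to the comparison the plan describes. The k = 6 case is what would follow if VISA-A and pain were added without adjustment.

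**After naming one primary comparison.** The error rate of the effectiveness claim returns to 5%. The detectable difference at 80% power (normal approximation, 20 per group) is (1.960 + 0.842) × √(2/20) = 0.89 SD. Bonferroni over six outcomes would use 0.05/6 = 0.0083 each, giving (2.638 + 0.842) × √(2/20) = 1.10 SD.

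**The case against.** The strongest reply is that the omission is less damaging than it looks. The paired tests are already tied to baseline versus the final examination, so a time point exists for them. This stands for those tests. It does not settle the group comparison, for which the visits and the deciding term are not stated.

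A reader might infer that a chance finding is likely. The figures do not support that. Six independent tests give 26.5%, and the risk passes one half only from 14 independent tests (ln 0.5 / ln 0.95 = 13.5). The plan describes no separate between-group tests at each visit that would reach that number.

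A reader might also count 6 outcomes × 2 groups = 12 paired tests and quote 1 − 0.95¹² = 46.0%. That figure requires no true change in any outcome in either treated group over 26 weeks. Since both groups train, a significant paired test would usually reflect real change, and it is not a claim about ESWT in any case.

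Nor does the text support saying that every parameter is tested for a treatment effect: that is so only for the baseline and within-group tests. It does not show that anyone will choose a conclusion after seeing the results; it shows that no rule prevents this. The document carries a registry number, and the registry record was not available, so the point is limited to this document.

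Finally, choosing VISA-A as primary is a judgement, and a sponsor interested mainly in structure could choose otherwise. That stands. The need to choose one outcome does not depend on which is chosen.

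**Conclusion.** The concern holds in a limited form. The document states no primary outcome, no primary time point for the group comparison, no multiplicity rule and no success criterion. The only between-group follow-up test covers an open set of morphological parameters at an unadjusted .05, and VISA-A and pain have only baseline and within-group tests.

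For the comparison as planned, the false-positive risk is about 12–14% with three parameters, or 18.5% with four if independent: roughly two and a half to four times nominal. It would be about 21–26% if all six assumed outcomes were tested between groups. These figures rest on the assumed SFA count, one deciding test per parameter, and correlations of 0 to 0.5; stronger correlation lowers them. The missing decision rule and the missing comparison of patient-reported outcomes do not depend on any of these percentages.

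**What to change.** Before the data are analysed, state the following in the Data analysis section.

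1. One primary outcome, visit and between-group test. For example, VISA-A at the week-26 final examination, Group A versus Group B, by analysis of covariance with baseline VISA-A as covariate.
2. Secondary outcomes, also compared between groups: the two pain ratings, tendon width, and one SFA parameter named in advance with its direction of improvement.
3. All other SFA parameters labelled exploratory.
4. The effectiveness conclusion based on the primary between-group comparison only, with the within-group paired tests treated as descriptive.
5. For any repeated-measures ANOVA that is kept, the visits included and the term that decides.

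**Cost.** One added analysis of data already collected at the initial and final examinations, with no new visits or patients. The sponsor can no longer headline whichever parameter turns out significant. Power is also a limit: the 0.89 SD computed above is a large difference, although baseline adjustment should reduce it to the extent that baseline predicts outcome. Naming one primary outcome costs less power than a Bonferroni correction across six.

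### Effect sizes are planned only for change within each arm; the randomised comparison is a significance test of morphological parameters, with no between-arm difference or confidence interval for any outcome

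*Combined protocol and SAP*

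**What the plan says.** The Data analysis section of the combined protocol and SAP contains three sets of comparisons.

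- **Between arms, at baseline.** Independent t-tests or Mann-Whitney tests "will be performed for each parameter to compare baseline values between groups". Their stated use goes no further than baseline.
- **Within each arm, over time.** Paired t-tests or Wilcoxon tests for each parameter, "evaluated in each group separately between baseline and final values". Effect sizes belong to these tests alone: Cohen's d "will be calculated for paired t-tests and biserial rank correlation for non-parametric Wilcoxon test".
- **Between arms, over time.** "Intergroup statistical significance between baseline and follow-up values of morphological parameters will be evaluated using two-way ANOVA with repeated measures", or a Friedman test. The criterion is p < .05.

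No confidence interval is mentioned, and no effect size is attached to the third set. VISA-A and the pain NRS are collected under Initial and final examination, but the third set covers morphological parameters only. On size, Study design and description says "It is estimated that at least 40 patients will participate", with no target difference, SD, power or dropout allowance.

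**The concern.** Both groups follow the same 12-week training and only group A adds ESWT, so the A-versus-B contrast is the one that isolates ESWT. Change within an arm also contains the training effect, the natural course and regression to the mean, and randomisation removes none of these from a before/after comparison. Followed exactly, the plan would quantify the contrast that randomisation does not protect and leave the one it does protect with a p value.

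Two things are at stake. For the morphological parameters, a reader would learn whether p fell below .05 but not how large the ESWT effect is or what range of effects the data allow. For VISA-A and NRS, the only planned post-baseline results are one before/after test and effect size per arm, which leaves nothing to look at except the two arms' values side by side.

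**Working it through.** **Inputs.** From the documents: at least 40 patients, two groups, significance at p < .05. Assumed, because the documents do not say: 1:1 allocation (20 per arm), two-sided testing, equal SD at baseline and follow-up, and a baseline/follow-up correlation rho of 0.3 to 0.8. The figure of 40 cannot be reproduced, since no target effect, SD or power is given.

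**1. How far two within-arm effect sizes drift apart when ESWT adds nothing.** Take a true paired d of 0.8 in both arms, d being mean change divided by the SD of change (an assumed scaling). In 200,000 simulated pairs of arms with n = 20 each, the difference between the two observed d values has an SD of 0.39. It exceeds 0.3 in either direction in about 43% of trials and 0.5 in about 19%.

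**2. Precision of the between-arm difference at 20 per arm.** In units of the SD of a single measurement:

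- change scores: half-width = t(0.975, 38) × √(2/20) × √(2(1 − rho))
- baseline-adjusted (ANCOVA): half-width = t(0.975, 37) × √(2/20) × √(1 − rho²)

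with t(0.975, 38) = 2.024, t(0.975, 37) = 2.026 and √(2/20) = 0.316. At rho 0.5: 2.024 × 0.316 × 1 = 0.640, and 2.026 × 0.316 × 0.866 = 0.555.

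| Assumed rho | Change score, ± SD | Baseline-adjusted, ± SD | Ratio of d: SD of change vs baseline SD |
|---|---|---|---|
| 0.3 | 0.757 | 0.611 | 0.85 |
| 0.5 | 0.640 | 0.555 | 1.00 |
| 0.7 | 0.496 | 0.458 | 1.29 |
| 0.8 | 0.405 | 0.384 | 1.58 |

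The last column is 1/√(2(1 − rho)). It shows how much the same mean change is rescaled by the choice of denominator for d.

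Fewer analysed patients widen the interval. In SDs of the quantity analysed, t × √(2/n) is 0.64 at 20 per arm, 0.68 at 18 and 0.72 at 16.

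**3. What a p value alone would leave open.** Again in SDs of the quantity analysed, with 20 per arm:

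- p = 0.05 corresponds to a difference of 0.64, 95% interval 0.00 to 1.28.
- p = 0.20 corresponds to 0.41, interval −0.23 to 1.05.

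Power (noncentral t) is 34% for a difference of 0.5, 69% for 0.8, 79% for 0.9 and 87% for 1.0.

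**4. The non-parametric route.** The Friedman test ranks repeated measurements within patients. It has no between-group factor, so it gives neither a test nor an estimate of A versus B.

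**The case against.** A reader might infer that 40 patients cannot support a conclusion in either direction. The documents do not support that. A significant group-by-time interaction would be evidence of a difference, power is 79% to 87% for differences of 0.9 to 1.0 SD, and 40 is given as a minimum. Only the weaker statement stands: significance would not give the size, and non-significance would not show absence.

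A reader might also infer that the planned d is inflated because it is divided by the SD of change. The plan does not state the denominator. Even with that scaling, there is inflation only for rho above 0.5; at 0.5 there is none and at 0.3 the value shrinks. Nor can the widest intervals be combined with the largest inflation, because a high rho narrows the interval. What stands is that the denominator is unspecified.

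It is fair to add that the plan nowhere says it will read p > .05 as no effect or compare the two within-arm effect sizes; how readers will behave is a prediction. Nothing bars the investigator from reporting group means and SDs, from which a reader could work out an unadjusted interval. But that leaves the main estimate to the reader, when the plan has already chosen to specify effect sizes and has attached them to the within-arm contrast.

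**Conclusion.** The point holds in this form: the plan specifies effect sizes for within-arm change, specifies none and no interval for the randomised contrast, and describes no post-baseline between-arm analysis for VISA-A or NRS. This follows from the text and needs no assumption.

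The size of the problem does rest on assumptions. With 20 per arm and a common true paired d of 0.8, an apparent gap above 0.3 between the arms would arise by chance in about 43% of trials. A between-arm interval would extend about 0.40 to 0.76 SD either side of the estimate on change scores, or 0.38 to 0.61 SD with baseline adjustment, over rho 0.8 down to 0.3. A larger enrolment would narrow these figures and dropout would widen them. Over most of this range, a non-significant result would leave moderate, and in many cases large, effects open.

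**What to change.** - For every parameter, VISA-A and NRS included, report the A-minus-B difference, adjusted for baseline, in the parameter's own units with its 95% confidence interval beside the p value.
- Name one visit in advance for this estimate, for example the 26-week final examination, so that three follow-up visits do not produce competing headline results.
- Estimate it by ANCOVA or another model with a group factor. For non-normal data, use a bootstrap or rank-based between-group interval in place of the Friedman test.
- State that p > .05 will not be reported as absence of an ESWT effect.
- Label within-arm effect sizes as descriptive and state the denominator of d.

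The cost is a short revision of the Data analysis section and a small additional analysis; no new patients, visits or measurements are needed. It is not free of work: ANCOVA is not the planned repeated-measures ANOVA, and no A-minus-B interval can be taken from a Friedman test. The other downside is that the intervals will show the trial's limited precision openly.
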